8.3. Exploratory Immunogenicity Analyses

Immunologic bridging analyses are outside the scope of this SAP.

Exploratory analyses covered in this SAP include summaries of GMTs, GMCs, seroconversion rates and seropositivity rates at the time of the second dose (sample collected prior to the dose) and one month after the second dose. Analyses will be performed for both ELISA and PBNA. Summaries will be repeated within each of the trial centers. Spaghetti plots of the antibody and titer results will be provided by study day and treatment group (Figure 13 through Figure 16). In addition, summaries of the GMC ratio one month after the second dose between the Cecolin® schedules will be generated, where the 0, 12 group and 0, 24 group will be compared (individually) to the 0, 6 group (Table 34).

GMCs/GMTs, seroconversion and seropositive rates after a single dose of Cecolin® or Gardasil® will be summarized at multiple timepoints. Arms will contribute the following timepoints

- Arm 1 (0, 6 Cecolin®): 6-month single dose for Cecolin®
- Arm 2 (0, 12 Cecolin®): 12-month single dose for Cecolin®
- Arm 3 (0, 24 Cecolin®): 24-month single dose for Cecolin®
- Arm 4 (0,6 Gardasil®): 6-month single dose for Gardasil®
- Arm 5 (0- Gardasil® and 24- Cecolin®): 24-month single dose for Gardasil®

These summaries will be contained in Table 26, Table 31, and Table 38. Additionally, single dose comparisons at 6- months (Arms 1 and 4) and 24- months (Arms 3 and 5) will be explored via the GMC ratios (Table 34).

In addition, in each arm, for both ELISA and PBNA HPV16 and HPV18, Antibody Kinetics modelestimate GMC/GMT from mixed models for repeated measures (MMNR9) will fit to log transformation of the concentration (or titres). Each model will include subject as random effect, visit and country as fixed effects and will assume compound symmetry for the covariance structure. As all subjects in the Per-Protocol population are seronegative at baseline, visit 1 will not be included in the model and presented as below LLQ. Fitted GMC/GMT and 95% CI will be presented in Table 46, Table 47 and in Figure 17 to Figure 19. The percentage decay at 18 months post-dose 2 relative to 1 month post-dose 2 for groups 1 and 4, estimated from the model, will also be presented in Table 46 and Table 47.

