4.5.1. Immunogenicity Variables

To evaluate immunogenicity of Cecolin® and Gardasil®, anti-HPV 16 and 18 IgG antibody measured by enzyme-linked immunosorbent assay (ELISA) and anti-HPV 16 and 18 serum neutralizing antibodies measured by pseudovirion-based neutralization assay (PBNA) will be used. For each treatment group, blood will be collected for immunologic testing for the primary endpoint at one month following second dose. Additional blood collections will occur at baseline, immediately prior to the administration of the 6-month, 12-month or 24-month dose, and 24 months after the first dose in Groups 1 and 4 for noninferiority comparison.

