5. SAMPLE SIZE CONSIDERATIONS

Immunogenicity:

It is anticipated that no more than 10% of subjects will be seropositive at baseline and that no less than 85% of subjects will be evaluable for the immunogenicity assessments; see Section 6.3 for definitions of the immunogenicity analysis populations.

The primary objective includes three non-inferiority comparisons of Cecolin® at 0 and 6 months, 0 and 12 months, or 0 and 24 months compared to Gardasil® at 0 and 6 months. To control the type I error for the three co-primary non-inferiority hypotheses a Bonferroni correction resulting in a one-sided alpha of 0.0083 and corresponding to 98.3% confidence intervals (CI) will be used. To account for the simultaneous assessment of serotypes 16 and 18, 95% power is required for each comparison to achieve 90% power overall for the primary objective (0.952 \approx 0.90).

Non-inferiority will be demonstrated if the lower bound of the 98.3% CI of the geometric mean concentration (GMC) ratio is greater than 0.5 for both HPV 16 and HPV 18. Assuming an IgG standard deviation of 0.65 of the log10 scale, adjustment for center, 10% baseline seropositive (see Section 3.3), and 15% dropout 205 subjects per arm will result in 90% power overall for the primary non-inferiority comparisons. The non-inferiority margin of 0.5 was selected in accordance with the WHO Technical Report Series #962.

A sample size of 205 in the mixed schedule Gardasil® at 0 months and Cecolin® at 24 months provides 96% power for similar non-inferiority comparisons to Gardasil® at 0 and 6 months for both serotypes at the one-sided alpha 0.025 level. Similarly, the 24-month comparison of the 0,6 Gardasil® and 0,6 Cecolin® groups has greater than 90% power for non-inferiority comparisons for both serotypes at the one-sided alpha 0.025 level.

Analyses of the PBNA data will be descriptive in nature. However, the 20% sub-sample of subjects, resulting in approximately 200 overall for relevant timepoints, will provide a lower bound above 0.6 for the 95% CI for a Spearman's rank correlation of 0.7 or higher.

Safety:

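### The antibody kinetics model imposes compound symmetry without justification or fallback, so its 95% CIs for visit GMCs and GMTs, and any CI for the decay, may be mis-sized

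*SAP*

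**What the plan says.** SAP Section 8.3 fits a separate model to log concentrations or titres in each arm, for ELISA and PBNA and for HPV 16 and 18. On the terms it states: "Each model will include subject as random effect, visit and country as fixed effects". On the covariance, the model "will assume compound symmetry for the covariance structure". Baseline is dropped: "visit 1 will not be included in the model and presented as below LLQ".

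Apart from baseline and the sample one month after dose 2, SAP Section 4.5.1 places the blood draws "immediately prior to the administration of the 6-month, 12-month or 24-month dose, and 24 months after the first dose in Groups 1 and 4". The model therefore sees three visits in Groups 1 and 4 (Visits 4, 6 and 7) and two in Groups 2, 3 and 5 (Visits 4 and 6).

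Two outputs are named. The first carries an interval: "Fitted GMC/GMT and 95% CI will be presented in Table 46, Table 47", with Figures 17 to 19. The second is "The percentage decay at 18 months post-dose 2 relative to 1 month post-dose 2 for groups 1 and 4, estimated from the model", also for Tables 46 and 47, with no interval mentioned.

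The SAP states one SD for planning and none by visit. It gives no between-visit correlation, no reason for compound symmetry, no fallback, no robust standard error and no check of the assumption.

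**The concern.** Compound symmetry assumes that girls vary equally at every visit and that every pair of visits is equally correlated. The plan's own schedule makes both doubtful:

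- Visit 4 is the level left after one dose, Visit 6 is one month after the second, and Visit 7 is 18 months after the second. A dose is given between Visits 4 and 6 and none between Visits 6 and 7.
- Protocol Appendix I puts these visits at Days 180, 210 and 730 for Groups 1 and 4, which is very uneven spacing.
- SAP Section 8 replaces values below the LLOQ by a single constant. If such values occur after baseline, the pre-dose-2 visit is the likeliest place, and its variance alone would change.

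At stake are the intervals in Tables 46 and 47 and Figures 17 to 19. SAP Section 8.2 also gives 95% CIs for visit GMCs in Table 26 and visit GMTs in Table 35. If variances differ by visit, one report could show differing intervals for the same quantity. The decay has no such second source, because it comes only from this model. The model serves the exploratory kinetic-modelling objective in SAP Section 3.1.3, which is meant to inform the dose interval.

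**Working it through.** **Sample size and SD.** SAP Section 5 supplies the only usable figures: "Assuming an IgG standard deviation of 0.65 of the log10 scale", and "15% dropout 205 subjects per arm will result in 90% power overall", with 10% seropositive at baseline. Evaluable girls per arm: 205 × 0.85 × 0.90 = 156.8. With margin log10(2) = 0.301, true ratio 1 and one-sided alpha 0.05/6 = 0.0083, power is 95.6% per HPV type and 0.956² = 91.4% for both. The required n is 153 evaluable, or 153/(0.85 × 0.90) = 200 randomised, against 205 planned. The plan's figure reproduces, and about 157 is a fair n for ELISA. For PBNA, about 20% of each arm is tested (SAP Section 4.4.2): 0.20 × 205 = 41, and 41 × 0.85 × 0.90 = 31.

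**Formulas.** With complete data, and ignoring the country term, a compound-symmetry fit uses v, the mean of the visit variances, and c, the mean of the pairwise covariances.

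- Visit mean: model SE √(v/n), true SE √(s_j²/n), ratio r = √(v/s_j²).
- Visit 7 minus Visit 6: model SE √(2(v − c)/n), true SE √((s6² + s7² − 2·s67)/n), where s67 is the covariance.
- Coverage of a nominal 95% CI: 2Φ(1.96·r) − 1.

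The ratio r does not contain n, so the error does not shrink in a larger trial.

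**One case in full, all SDs and correlations assumed.** SDs 0.65/0.45/0.55 at Visits 4/6/7; correlations 0.5 (4-6), 0.6 (4-7), 0.8 (6-7).

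- v = (0.4225 + 0.2025 + 0.3025)/3 = 0.3092, so the common SD is 0.556. Ratios: 0.556/0.65 = 0.86, 0.556/0.45 = 1.24, 0.556/0.55 = 1.01.
- c = (0.1463 + 0.2145 + 0.1980)/3 = 0.1863. Model variance of the difference: 2 × (0.3092 − 0.1863) = 0.2458 (per n). True: 0.2025 + 0.3025 − 0.3960 = 0.1090. Ratio: √(0.2458/0.1090) = 1.50.
- In practical terms at n = 156.8, the Visit 6 GMC would be shown as ×/÷ 10^(1.96 × 0.556/12.52) = 1.22, where 10^(1.96 × 0.45/12.52) = 1.18 is right.

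**Range, three-visit arms (all inputs assumed).**

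| SDs, V4/V6/V7 | Correlations, 4-6/4-7/6-7 | Visit coverage, % | Decay SE ratio | Decay coverage, % |
|---|---|---|---|---|
| 0.65/0.65/0.65 | 0.6/0.6/0.6 | 95.0/95.0/95.0 | 1.00 | 95.0 |
| 0.65/0.65/0.65 | 0.5/0.6/0.8 | 95.0/95.0/95.0 | 1.35 | 99.2 |
| 0.55/0.45/0.50 | 0.6/0.6/0.6 | 92.6/97.1/95.1 | 1.06 | 96.2 |
| 0.65/0.45/0.55 | 0.6/0.6/0.6 | 90.6/98.5/95.2 | 1.12 | 97.1 |
| 0.65/0.45/0.55 | 0.5/0.6/0.8 | 90.6/98.5/95.2 | 1.50 | 99.7 |
| 0.65/0.40/0.50 | 0.4/0.5/0.85 | 88.8/99.0/96.1 | 1.94 | about 100 |
| 0.40/0.65/0.50 | 0.7/0.7/0.5 | 99.0/88.8/96.1 | 0.82 | 89.1 |

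**Two-visit arms.** There is only one pair, so equal correlation restricts nothing. With assumed SDs 0.65/0.45, v = 0.3125 and the common SD is 0.559. The ratios are 0.86 and 1.24, and coverage is 90.8% and 98.5%. For the change between visits, 2(v − c) equals s4² + s6² − 2·s46 exactly, so its SE is right with complete data.

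**Simulation.** 600 runs per scenario, with a country effect and 2%, 3% and 10% missing at Visits 4, 6 and 7. At n = 157 the fifth row gave 89.5/97.8/94.5% for the visits and 99.5% for the decay. The last row gave 99.3/88.3/95.3% and 87.0%. Bias in the log10 decay was below 0.005 in every run, which is about 1% of the Visit 7 to Visit 6 ratio (10^0.005 = 1.01).

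**The case against.** The strongest reply is that nothing in the documents shows the assumption to be false. The only SD is a single 0.65. With equal SDs and correlations the intervals are exactly right, and with equal SDs alone the visit CIs are still right. That stands. A reader might infer that the CIs in Tables 46 and 47 are wrong, but the documents support only that they may be.

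A reader might also infer that the plan promises a decay CI, or that the reported decay will be biased. Neither is supported. Section 8.3 names an estimate only, and the shells of Tables 46 and 47 are not in the text available, so whether an interval is planned is unknown. With complete data the estimated visit difference is the same under either covariance, and with the simulated missing visits it barely moved. Nor is compound symmetry always conservative for the decay: the SE ratio ran from 0.82 to 1.94.

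Finally, the model is exploratory. Visit GMCs and GMTs with CIs also appear in Tables 26 and 35, and the Month 24 comparison of Groups 1 and 4 has its own ratio and CI in Table 30. That limits the importance of the point. It gives no reason to keep an unsupported restriction that costs almost nothing to remove.

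**Conclusion.** The point holds as a conditional one of low severity. The SAP imposes compound symmetry on visits that represent different immune states, and offers neither a justification nor a way out.

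- **Visit GMCs and GMTs, all arms:** if variances differ by visit, the model-based 95% CIs are mis-sized in either direction. Assumed scenarios gave coverage from about 89% to 99%.
- **Decay, Groups 1 and 4:** if variances or correlations differ, any SE or CI attached to it is mis-sized. Assumed scenarios gave coverage from about 89% to nearly 100%. The point estimate is essentially unaffected.
- **Groups 2, 3 and 5:** only the equal-variance restriction matters.

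Every visit-specific SD and correlation behind these ranges is assumed, and the ranges include no error at all. The calculation shows what could happen and does not predict this trial's data. No non-inferiority conclusion is touched.

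**What to change.** In SAP Section 8.3, replace compound symmetry and the random subject effect by an unstructured within-subject covariance: a REPEATED statement by visit within subject, no separate random subject term, and Kenward-Roger degrees of freedom. Name heterogeneous compound symmetry as the fallback on non-convergence. The fallback frees the variances but still forces equal correlations, so a decay CI taken from it should carry that caveat. With two visits the fallback is the same model.

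The wording also needs tidying. A random subject effect and compound symmetry describe the same structure when the within-girl covariance is positive, and fitting both is over-parameterised.

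If a CI for the decay is to be reported, say so and take it from this model.

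The cost is a small change to the SAS code. The unstructured matrix has 6 parameters instead of 2 with three visits, and 3 instead of 2 with two. That is feasible with about 157 girls per arm for ELISA and about 31 for PBNA, where the Kenward-Roger adjustment matters most. Compound symmetry is a special case of the unstructured matrix, so little precision is lost if it happens to be true.

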9. SAFETY EVALUATION

All safety assessments will take place in the total vaccinated population, according to the treatment received and will be summarized overall and by study site. All subject-level percentages (solicited/unsolicited AEs etc.) will be supplemented with two-sided 95% CIs computed via the Clopper-Pearson method. Summaries will include all events occurring on or after the date of each vaccination. Individual summaries (denominators for percentages) will be limited to the number of subjects within the appropriate analysis population with data available for analysis for the given endpoint.

9.1. Adverse Events

A secondary objective of this study is safety of Cecolin[®] vaccination. All safety assessments will take place in the total vaccinated population, according to the treatment received and will be summarized overall and by study site. All subject-level percentages (solicited/unsolicited AEs etc.) will be supplemented with two-sided 95% CIs computed via the Clopper-Pearson method. Summaries will include all events occurring on or after the date of each vaccination.

9.1.1. Reactogenicity

- Reactogenicity will be assessed according to immediate (at least 30 minutes post-vaccination) and • delayed reactogenicity (through Day 7), after any and each vaccination. Delayed and immediate solicited AEs will be summarized by category (local/systemic), by reaction and by postvaccination time point, overall and by site (Table 48 through Table 59). Solicited AEs will also be summarized by severity within reaction and within category by post-vaccination time point and by site and by vaccine type (Table 60 through Table 69), and by severity and reaction according to post-vaccination day by post-vaccination time point and by site. The summaries will present each severity up to the maximum severity reported for each reaction/day combination (Table 70 through Table 75). Each subject will be counted only once under the maximum severity of each reaction and/or category, where relevant, in these summaries. Analyses involving severity will include those graded ≥ 2 . Summaries of solicited AEs observed across the solicitation period will be accompanied by a two-sided Fisher exact test p-value for a difference among groups, for both local and systemic events (overall and by reaction), as well as across these events (overall). Reactogenicity events ongoing at 7 days post-vaccination will be listed (Listing 12). Duration of reactogenicity events will be summarized by reaction and time period and by site (after any dose, after first dose and after second dose) (Table 76 through Table 81).
- Measured injection site features will be summarized by group and post-vaccination time point, including but not limited to erythema/redness, swelling, and induration (Table 82 through Table 85).

Individual listings of solicited AEs ongoing at 7 days after any dose will be generated (Listing 12).

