#### Safety:

There is greater than 90% power to observe a severe or serious AE at a rate of  $\geq 0.4\%$  among the 615 subjects that will receive Cecolin® in month 0 and a rate of  $\geq 0.6\%$  among the 410 receiving at least one dose of Gardasil®. Within any arm there is a greater than 90% probability of observing at least one severe or serious AE with a  $\geq 1.2\%$ . The upper bounds of the 95% CIs implied if no AEs are observed are show in Table 2.

Table 2: Detectable rates of AEs and 95% CI upper bounds if no events are observed.

Sample size		Upper bound of 95% confidence interval if no events are observed
615	0.4%	0.6%
410	0.6%	0.9%
205	1.2%	1.8%

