# 11.5.2.2.2 Reactogenicity

Reactogenicity will be assessed according to immediate (at least 30 minutes post-vaccination) and delayed reactogenicity (within 8 days post-vaccination), as well as combined after each vaccination. Solicited AEs will be summarized overall, by category (local/systemic), by reaction, and by severity within reaction and within category, and by severity and reaction according to post-vaccination day, where each subject is counted once under the maximum severity of each reaction and/or category, where relevant. Analyses involving severity will include those graded ≥2. Summaries of solicited AEs observed across the solicitation period will be accompanied by a two-sided Fisher exact test p-value for a difference among groups, for both local and systemic events (overall and by reaction), as well as across these events (overall). Reactogenicity events ongoing at 7 days post-vaccination will be listed. Duration of reactogenicity events will be summarized by reaction.

Measured injection site features will be summarized by group and post-vaccination time point, including but not limited to pain, erythema/redness, swelling/induration, abscess and pruritis.

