4.5.2.1. Solicited Adverse Events

Solicited AEs are pre-specific local and systemic adverse events that are common or known to be associated with vaccination that are actively monitored as indicators of vaccine reactogenicity. For this trial, solicited AEs will be assessed by study staff 30 minutes after each vaccination and then daily for 7 days by the participants (data to be collected for Days 1 through 7). Participants will be provided a memory aid to record the presence or absence of solicited AEs, severity of the solicited AEs and use of concomitant medication.

The following specific solicited adverse events will be monitored for this trial:

Local Reactions:

• Pain, erythema/redness, swelling, induration, pruritus, abscess.

General/Systemic Reactions:

• Fever, headache, vomiting, nausea, fatigue, chills, muscle pain, cough, diarrhea, dizziness, allergic dermatitis, rash, syncope and anorexia.

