There is greater than 90% power to observe a severe or serious AE at a rate of $\geq 0.4\%$ among the 615 subjects that will receive Cecolin[®] in month 0 and a rate of $\geq 0.6\%$ among the 410 receiving at least one dose of Gardasil[®]. Within any arm there is a greater than 90% probability of observing at least one severe or serious AE with a $\geq 1.2\%$. The upper bounds of the 95% CIs implied if no AEs are observed are shown in Table 2.

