6. GENERAL STATISTICAL CONSIDERATIONS

6.1. General Principles

All analyses will be grouped by vaccination arm. In general, all data will be listed, sorted by treatment group, site and subject, and when appropriate by visit number within subject. All summary tables will be structured with a column for each treatment group (including a column for all participants) and will be annotated with the total population size relevant to that table, including any missing observations.

Except where otherwise indicated, summary statistics will be composed of the mean, standard deviation, 1st, 2nd, and 3rd quartile, and the minimum and maximum for continuous variables. For categorical variables, the count and proportion will be presented.

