6.8. Multiple Comparisons/Multiplicity

The primary objective includes three non-inferiority comparisons of Cecolin[®] at 0 and 6 months, 0 and 12 months, and 0 and 24 months with Gardasil[®] at 0 and 6 months. To control the type I error rate for the three co-primary non-inferiority hypotheses, a Bonferroni correction resulting in a one-sided alpha of 0.0083 and corresponding to 98.3% confidence intervals (CI) will be used.

No other adjustments for type I error rate will be made.

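### Optional improvement: for first-dose solicited AEs, one Cecolin (Groups 1-3) versus Gardasil (Groups 4-5) Fisher test would use the data better than a test across five arms

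*SAP*

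**What the plan says.** SAP 9.1.1 summarises solicited AEs after any and after each vaccination. Summaries over the solicitation period are to be "accompanied by a two-sided Fisher exact test p-value for a difference among groups", for each reaction, for any local, for any systemic, and overall. Protocol 11.5.2.2.2 has the same rule: "two-sided Fisher exact test p-value for a difference among groups". Neither sentence says how many groups are compared. The five-arm reading comes from SAP 6.1, which groups all analyses by vaccination arm and adds: "All summary tables will be structured with a column for each treatment group".

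The plan pools arms by first product in one place, the safety sample-size text. SAP section 5 gives detection probabilities "among the 615 subjects that will receive Cecolin" at month 0, and Protocol 11.3 does so "among the 410 receiving at least one dose of Gardasil". Those are single-sample statements about seeing at least one severe or serious event. They do not specify a comparison of products.

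The secondary safety endpoints (Protocol 2.3.2.2, SAP 3.2.2.2) are counts of girls in each arm. SAP section 9 attaches Clopper-Pearson intervals to the percentages. On multiplicity, SAP 6.8 covers the three primary comparisons and then says: "No other adjustments for type I error rate will be made".

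**The concern.** At the first dose, the five arms carry only two treatments. A five-group test has four degrees of freedom. One of them carries the Cecolin-Gardasil contrast, and the other three compare arms that have so far been treated identically. Two things follow. Power for a true product difference is diluted. A small five-group p-value also does not by itself show that the products differ, because chance variation among identically treated arms can contribute to it.

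Cecolin safety is a secondary objective. The first dose is the only point at which all 1,025 girls inform a randomised product comparison free of dose interval and of the mixed schedule. What is at stake is how well the trial uses those data for reactogenicity. No primary or secondary conclusion depends on this p-value.

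**Working it through.** **Step 1: the plan's own safety figures.** The probability of at least one event is 1 - (1 - p)^n. The upper 95% bound with no events is 1 - 0.025^(1/n).

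| n | p | P(at least one) | Upper bound | Protocol Table 2 bound |
|---|---|---|---|---|
| 615 | 0.4% | 91.5% | 0.60% | 0.6% |
| 410 | 0.6% | 91.5% | 0.90% | 0.9% |
| 205 | 1.2% | 91.6% | 1.78% | 1.8% |

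The stated figures reproduce, and 615 = 3 x 205 and 410 = 2 x 205 are the first-dose product totals.

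**Step 2: inputs for the comparison.** There are 205 girls per arm (SAP 4.1). A two-sided 0.05 level is assumed, because none is stated for this test. Three Cecolin rates are anchored in the Protocol: 34% (injection-site pain, adult phase 3 trial, section 1.5.3), 8% (mid-range of the 7-9% for headache and fatigue, adult phase 2 trial, section 1.5.2) and 54.2% (solicited AEs, two-dose girls aged 9-14, section 1.5.2). None is a first-dose rate, so 20%, 10% and 5% were added to cover lower values. All Gardasil rates are assumptions.

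**Step 3: noncentrality.** With equal rates within a product, both tests have the same noncentrality, 1025 x 0.6 x 0.4 x (pC - pG)^2 / [pbar(1 - pbar)], where pbar = 0.6 pC + 0.4 pG. They differ in degrees of freedom: 4 (critical value 9.488) against 1 (critical value 3.841). For 80% power these need noncentralities of 11.94 and 7.85, and 11.94 / 7.85 = 1.52.

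Worked case, 34% v 26%: pbar = 0.308, and 246 x 0.0064 / (0.308 x 0.692) = 7.39. Power is 57% on 4 df and 78% on 1 df.

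**Step 4: simulation of the Fisher tests.** There were 20,000 simulated trials per row. The five-group exact test used Monte Carlo p-values; the two-group tests were exact.

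| Cecolin v Gardasil | Five-group | Pooled 615 v 410 | Group 1 v Group 4 |
|---|---|---|---|
| 34% v 29% | 23% | 38% | 17% |
| 34% v 26% | 57% | 77% | 38% |
| 34% v 24% | 80% | 93% | 57% |
| 34% v 42% | 51% | 72% | 34% |
| 54.2% v 46% | 51% | 73% | 36% |
| 20% v 14% | 48% | 69% | 32% |
| 20% v 13% | 65% | 83% | 42% |
| 10% v 5% | 66% | 83% | 42% |
| 8% v 4% | 54% | 73% | 32% |
| 5% v 2% | 50% | 70% | 28% |

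Before rounding, the gain from pooling runs from 12.8 to 21.7 points. With no true difference the five-group and pooled tests hold their level: 5.2% and 4.6% at 34%, 4.8% and 4.1% at 8%.

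**Step 5: where the gain is small.** By the Step 3 approximation, five-group to pooled: 34% v 32%, 7% to 10%; 34% v 31%, 11% to 17%; 1% v 0.5%, 9% to 14%; 34% v 22%, 93% to 98%; 20% v 10%, 95% to 99%. In a separate simulation of 4,000 trials, 30% v 20% gave 84% to 95%, a gain of 11 points.

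**Step 6: number of p-values.** The local reactions are "Pain, erythema/redness, swelling, induration, pruritus, abscess", which is 6. The systemic ones are "Fever, headache, vomiting, nausea, fatigue, chills, muscle pain, cough, diarrhea, dizziness, allergic dermatitis, rash, syncope and anorexia", which is 14. Adding any local, any systemic and any reaction gives 6 + 14 + 3 = 23. If both sets of p-values were kept, 23 x 0.05 = 1.15 of the extra ones would be expected below 0.05 by chance. Repeating the set at each of two sites would make 69, or about 3.5.

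**The case against.** The strongest reply is that this is a preference. The endpoints are defined per arm, the tables match them, the safety plan is mainly estimation with confidence intervals, and the p-values are unadjusted supplements. No between-product hypothesis or power target is stated. All of that stands. A reader might infer that the planned test is wrong or that the trial is underpowered for safety; the documents support neither.

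The five-arm reading is itself an inference from SAP 6.1. SAP 6.3.2 assigns safety groups by the product received on Day 1, SAP 9.1.1 also plans severity summaries by vaccine type (Tables 60-69), and the table shells were not supplied. A product-level p-value may already exist there. The five-arm reading is the more natural one, but it is not certain.

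The power gain depends on the scenario, as Step 5 shows, so 13 to 22 points cannot be quoted as a general figure. The comparison is randomised but not blinded: SAP 4.4.3 states open label, and girls record reactions on a memory aid. A more powerful test is also more sensitive to reporting bias.

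A reader might go further and infer that the Day 1 rule spoils the five-arm tables, or counts Group 5's Cecolin second-dose reactions under Gardasil. The text does not show this. The natural reading is that girls stay in their randomised arm unless given a wrong product, which leaves those tables sound. Misattribution would arise only if the Day 1 rule were applied to the vaccine-type tables, and those shells may settle it.

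**Conclusion.** The point holds as an optional, low-cost improvement. On the natural reading, the first-dose Fisher test spreads a two-product contrast over five arms, and for 80% power it needs about 1.5 times the noncentrality of the pooled test. The gain is roughly 13 to 22 power points where five-group power is about 20-80%, and only a few points where power is very low or above 90%. In terms of the difference detectable with 80% power (chi-square approximation), pooling lowers it from 10.1 to 8.2 points at a Cecolin rate of 34%, from 8.2 to 6.8 at 20%, and from 5.2 to 4.3 at 8%.

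This rests on a 0.05 level, assumed Gardasil rates, Cecolin rates that are not first-dose rates, and a common first-dose rate in arms given the same product, which the design supports. It applies to the first dose only, because Group 5 changes product at dose 2. It also applies to the final analysis only, because the interim (SAP 6.6.1) covers Groups 1 and 4 alone.

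**What to change.** In SAP 9.1.1, for the final analysis and the overall (not by-site) first-dose solicited-AE tables:

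- Make the p-value a two-sided Fisher exact test of Cecolin (Groups 1-3) versus Gardasil (Groups 4-5), by product given on Day 1, in place of the five-group first-dose p-value.
- Keep the per-arm columns and Clopper-Pearson intervals as the descriptive summaries of the endpoints.
- Label the p-values as unadjusted, and note that the trial is open-label and the reactions are self-reported.
- Record the change in SAP section 12.

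Separately, and only as a clarification, ask the sponsor to say in the text how vaccine type is defined for Group 5's second dose, or to refer to the shells of Tables 60-69 if they already do so.

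The cost is a small change to SAP wording and table programming, with no new data. If the pooled p-values replace the five-group ones, the number of tests does not rise. If both are kept, there are 23 extra unadjusted p-values.
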